#### **10.3.6 Non-dose escalation, non-quarterly visits occurring before Week 26**

The following assessments are to be completed:

- Abbreviated physical exam: within 24 hours prior to olipudase alfa infusion (pre-infusion).
- Body weight, height, BMI: within 24 hours prior to olipudase alfa infusion (pre-infusion).
- Vital signs: Before (within 30 minutes prior) infusion, halfway through infusion, and after infusion ( $\pm 10$  minutes). Postinfusion vital signs are measured every 30 minutes for the first 2 hours, hourly for 2 to 6 postinfusion, and then once every 8 hours until the patient is discharged ( $\pm 10$  minutes).
- Liver function testing: within 24 hours prior to olipudase alfa infusion (pre-infusion).
- Urine  $\beta$ -hCG pregnancy test: within 24 hours prior to olipudase alfa infusion (pre-infusion), every 4 weeks.
- Safety biomarkers: as indicated by age cohort in [Section 1.3](#) and [Section 1.4](#), within 24 hours prior to olipudase alfa infusion (pre-infusion).
- Plasma and/or DBS sphingomyelin and metabolites: as indicated by age cohort in [Section 1.3](#) and [Section 1.4](#), within 24 hours prior to olipudase alfa infusion (pre-infusion).
- Immunogenicity samples: every 2 weeks from Day 1/Week 0 through Week 16 (pre-infusion).

#### **10.3.7 Non-dose escalation, non-quarterly visit occurring after Week 26**

The following assessments are to be completed:

- Abbreviated physical exam: within 24 hours prior to olipudase alfa infusion (pre-infusion).
- Body weight, height, BMI: within 24 hours prior to olipudase alfa infusion (pre-infusion).
- Vital signs: Before (within 30 minutes prior) infusion, halfway through infusion, and after infusion ( $\pm 10$  minutes). Postinfusion vital signs are measured every 30 minutes for the first 2 hours, hourly for 2 to 6 hours postinfusion, and then once every 8 hours until the patient is discharged ( $\pm 10$  minutes).
- Urine  $\beta$ -hCG pregnancy test: within 24 hours prior to olipudase alfa infusion (pre-infusion), every 4 weeks.

### **10.3.8 Visit procedures at Week 64**

The following assessments are to be completed:

- Abbreviated physical exam: within 24 hours prior to olipudase alfa infusion (pre-infusion).
- Body weight, height, BMI: within 24 hours prior to olipudase alfa infusion (pre-infusion).
- Vital signs: Before (within 30 minutes prior) infusion, halfway through infusion, and after infusion ( $\pm 10$  minutes). Postinfusion vital signs are measured every 30 minutes for the first 2 hours, hourly for 2 to 6 postinfusion, and then once every 8 hours until the patient is discharged ( $\pm 10$  minutes).
- Clinical laboratory samples:
  - Liver function testing, clinical chemistry and coagulation: as indicated by age cohort in [Section 1.3](#) and [Section 1.4](#). Preinfusion samples to be collected within 24 hours prior to olipudase alfa infusion.
  - Urinalysis: within 24 hours prior to olipudase alfa infusion (pre-infusion).
- Urine  $\beta$ -hCG pregnancy test: within 24 hours prior to olipudase alfa infusion (pre-infusion).
- Safety biomarkers: as indicated by age cohort in [Section 1.3](#) and [Section 1.4](#), within 24 hours prior to olipudase alfa infusion (pre-infusion).
- Plasma and/or DBS sphingomyelin and metabolites: as indicated by age cohort in [Section 1.3](#) and [Section 1.4](#), within 24 hours prior to olipudase alfa infusion (pre-infusion).
- Immunogenicity samples: within 24 hours prior to olipudase alfa infusion (pre-infusion).
- Efficacy biomarkers: within 24 hours prior to olipudase alfa infusion (pre-infusion).
- Lipid profile: within 24 hours prior to olipudase alfa infusion (pre-infusion).
- Bone biomarkers: as indicated by age cohort in [Section 1.2](#), within 24 hours prior to olipudase alfa infusion (pre-infusion).

### **10.3.9 Alcohol consumption**

Patients must be willing to abstain from the use of alcohol for 1 day before and 3 days after each olipudase alfa infusion for the duration of the treatment period. Note: blood alcohol levels are not required.

Patients should be counseled to limit alcohol consumption for the entire duration of the study: male patients to a maximum of 30 g alcohol per day; female patients to a maximum of 15 g alcohol per day. Per the investigator's discretion, patients who fail to limit alcohol may be discontinued from the study.

### **10.3.10      Pregnancy**

Pregnancy will lead to permanent treatment discontinuation in all cases. No studies of olipudase alfa have been conducted in pregnant women. To ensure patient safety for this study, all female patients of childbearing potential must have a negative serum  $\beta$ -hCG pregnancy test at screening and before undergoing any further assessments and procedures. In addition, these patients are required to have a negative urine  $\beta$ -hCG pregnancy test every 4 weeks before undergoing visit specific assessments and receiving olipudase alfa.

Every effort should be made to prevent pregnancy during this study. Female patients of childbearing potential and male patients are required to practice true abstinence in line with their preferred and usual lifestyle or use two acceptable effective methods of contraception, a barrier method such as a condom or occlusive cap (diaphragm or cervical/vault cap) with spermicidal foam/gel/film/cream/suppository and an established non-barrier method such as oral, injected, or implanted hormonal methods, an intrauterine device or intrauterine system for the duration of the study.

### **10.4    DEFINITION OF SOURCE DATA**

Source data includes all information in original records and certified copies of original records of clinical findings, observations, or other activities necessary for the reconstruction and evaluation of the trial. Source data are contained in source documents.

Source documents are original documents, data and records (eg, hospital records, clinical and office charts, laboratory reports and notes, memoranda, patient diaries or evaluation checklists, pharmacy dispensing records, recorded data from automated instruments, copies or transcripts certified after verification as being accurate and complete, microfiches, photographic negatives, microfilm or magnetic media, X-rays, patient files, and records kept at the pharmacy, at the laboratories, and at medical-technical departments) involved in the clinical study. Source documentation must be maintained to support information provided in the e-CRF.

### **10.5    HANDLING OF TEMPORARY OR PERMANENT TREATMENT DISCONTINUATION**

The IMP should be continued whenever possible. In case the IMP is stopped, it should be determined whether the stop can be made temporarily; permanent IMP discontinuation should be a last resort. Any IMP discontinuation should be fully documented in the source and e-CRF. In any case, the patient should remain in the study as long as possible.

Pregnancy will lead to treatment discontinuation in all cases.

### **10.5.1 Temporary treatment discontinuation with investigational medicinal product(s)**

Temporary treatment discontinuation decided by the investigator corresponds to more than 1 infusion not administered to the patient.

Temporary treatment discontinuation (also referred to as treatment interruption) may be considered by the investigator because of suspected AEs.

Re-initiation of treatment with the IMP will be done under close and appropriate clinical/and or laboratory monitoring once the investigator has considered to his/her best medical judgment that the selection criteria for the study are still met (refer to [Section 7.1](#) and [Section 7.2](#)). Before re-initiation of treatment, the sponsor must be consulted to determine the starting dose and if dose escalation is required (see [Section 8.3.3](#) and [Section 8.3.4](#)).

For all temporary treatment discontinuations, the duration should be recorded by the investigator in the appropriate screens of the e-CRF.

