## 7 SELECTION OF PATIENTS

### 7.1 INCLUSION CRITERIA

To enter this study, patients must fulfill the following criteria:

- I 01. The patient and/or patient's parent(s)/legal guardian(s) must provide written informed assent/consent prior to any protocol-related procedures being performed.
- I 02. The patient is male or female <18 years of age on the date of signed informed assent/consent.
- I 03. The patient has documented deficiency of ASM consistent with NPD, as measured in peripheral leukocytes, cultured fibroblasts, and/or lymphocytes.
- I 04. The patient has a spleen volume  $\geq 5$  multiples of normal (MN) measured by magnetic resonance imaging (MRI); patients who have had partial splenectomies will be allowed if the procedure was performed  $\geq 1$  year before screening and the residual spleen volume is  $\geq 5$  MN.
- I 05. The patient's height is -1 Z-score or lower.
- I 06. Female patients of childbearing potential must have a negative serum pregnancy test for beta-human chorionic gonadotropin ( $\beta$ -hCG).
- I 07. Female patients of childbearing potential and male patients are required to practice true abstinence in line with their preferred and usual lifestyle or use two acceptable effective methods of contraception, a barrier method such as a condom or occlusive cap (diaphragm or cervical/vault cap) with spermicidal foam/gel/film/cream/suppository and an established non-barrier method such as oral, injected, or implanted hormonal methods, an intrauterine device or intrauterine system for the duration of the study.

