### 7.2 EXCLUSION CRITERIA

Patients who have met all the inclusion criteria listed in [Section 7.1](#) will be screened for the following exclusion criteria:

- E 01. The patient has received an investigational drug within the 30 days before study enrollment.
- E 02. The patient has any of the following medical conditions:
  - a) An active, serious, intercurrent illness;
  - b) Active hepatitis B or hepatitis C infection;

- c) Infection with human immunodeficiency virus (HIV);
- d) Cirrhosis (determined by clinical evaluation);
- e) Significant cardiac disease (eg, clinically significant arrhythmia, moderate or severe pulmonary hypertension or valvular dysfunction, or <40% left ventricular ejection fraction by echocardiogram);
- f) Malignancy diagnosed within the previous 5 years (except basal cell carcinoma);
- g) Any other extenuating circumstance that can significantly interfere with study compliance, including all prescribed evaluations and follow-up activities.

- E 03. The patient has acute or rapidly progressive neurological abnormalities.
- E 04. The patient is homozygous for *SMPD1* gene mutations R496L, L302P, and fs330 or any combination of these 3 mutations.
- E 05. The patient has delayed gross motor skills.
- E 06. The patient has had a major organ transplant (eg, bone marrow, liver).
- E 07. The patient requires use of invasive ventilatory support.
- E 08. The patient requires use of noninvasive ventilatory support while awake and for >12 hours a day.
- E 09. The patient, in the investigator's opinion, is unable to adhere to the requirements of the study.
- E 10. The patient has a platelet count <60 × 10^3/µL (based on the average of 2 screening samples obtained greater than 24 hours apart).
- E 11. The patient has alanine aminotransferase or aspartate aminotransferase >250 IU/L or total bilirubin >1.5 mg/dL.
- E 12. The patient has an international normalized ratio (INR) >1.5.
- E 13. The patient is unwilling or unable to abstain from ingesting alcohol the day before through 3 days after each infusion of olipudase alfa during the treatment period. Measuring alcohol concentration in blood is not required.
- E 14. The patient is scheduled during the study for in-patient hospitalization including elective surgery.
- E 15. The patient requires medication(s) that may decrease olipudase alfa activity (eg, fluoxetine, chlorpromazine; tricyclic antidepressants [eg, imipramine, or desipramine]).
- E 16. The patient is breast-feeding.

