#### 9.1.1 Physical examination

Complete physical examinations will be completed as indicated in [Section 1.2](#) and will include the following observations/measurements: general appearance, examination of the skin; head, eyes, ears, nose, and throat; lymph nodes; heart, lungs, and abdomen; extremities and joints and body mass index. The patient's weight will be measured without shoes and wearing the lightest possible clothing. At visits where height is measured, the patient will be measured without shoes. While patient height is included as part of the physical examination, z-score for height will be evaluated as an exploratory efficacy parameter.

An abbreviated physical examination will assess only the general appearance of the patient and is only required when a complete exam is not indicated.

Whenever possible, the same physician should perform the physical examination at all study visits.

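### Protocol 10.5.1 re-applies the entry criteria at restart without exempting height (I 05) or spleen volume (I 04), so read literally it could withhold re-dosing from a child who improved

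*Protocol*

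**What the plan says.** Protocol 10.5.1 defines an investigator-decided temporary discontinuation as more than 1 infusion not given, and says it may be considered because of suspected adverse events. Treatment may restart under close monitoring "once the investigator has considered to his/her best medical judgment that the selection criteria for the study are still met", with a reference to Sections 7.1 and 7.2. No criterion is exempted. The next sentence requires the sponsor to be consulted before restart, on the starting dose and on whether escalation is needed.

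Section 7.1 opens with "To enter this study, patients must fulfill the following criteria". Its I 05 requires that the patient's "height is -1 Z-score or lower". I 04 requires a spleen volume of at least 5 MN by MRI. Both quantities are also outcomes: Protocol 9.1.1 states that the "z-score for height will be evaluated as an exploratory efficacy parameter", and spleen volume in MN is among the exploratory efficacy endpoints.

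Section 10.5 says the product should be continued whenever possible and treats permanent discontinuation as a last resort.

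**The concern.** A recheck at restart makes sense for criteria that protect the patient, such as pregnancy, liver tests or a prohibited medication. It makes less sense for criteria that only ensure the child is ill enough to enrol. If treatment works, height Z-score rises and spleen volume falls, so a child who responds moves towards failing I 05 and I 04. A site applying 10.5.1 as written could then conclude that the criteria are no longer met and withhold drug from a patient who is benefiting.

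What is at stake is mainly that child's continuity of treatment, in a disease for which Protocol 4.1 says only palliative treatment exists. A second risk is that sites handle the same facts differently. Loss of efficacy data would be secondary.

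**Working it through.** The plan gives no figure on this point, so the check is mainly a comparison of texts, with two small illustrations.

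**1. Which criteria can fail later?** Several are fixed in time and cannot change meaning at restart:
- I 02 (age) is judged "on the date of signed informed assent/consent".
- E 01 (investigational drug) looks back "within the 30 days before study enrollment".
- E 10 (platelets) is "based on the average of 2 screening samples obtained greater than 24 hours apart".

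The I 05 and I 04 thresholds carry no such anchor. The only date in I 04 concerns when a partial splenectomy was done. For these two, asking whether the criterion is still met naturally means using current values.

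**2. Would the site have the values?**
- *Height.* SAP 2.8.2 has height collected at screening and within 24 hours before every infusion visit through Week 64, so a current height is available at any restart.
- *Spleen.* MRI is scheduled at screening, Week 26 and Week 52, or at withdrawal (SAP 2.8.1). The on-treatment scans are within 7 days after the infusion (Protocol 10.3.5). SAP 2.8.1 says the vendor gives the site an MN value for screening; other volumes are collected in cm³ and converted for analysis. Neither document says an on-treatment MN value goes back to the site.

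**3. How far from the height line?** A child entering at Z-score z₀ fails I 05 once the gain exceeds -1 - z₀.
- z₀ = -1.0: any gain.
- z₀ = -1.2: a gain above 0.2.
- z₀ = -2.0: a gain above 1.0.

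The documents give no prior height result, so the likely gain is unknown. SAP 2.8.2 does tabulate a category above -1 at Weeks 12 to 52, so the planned tables allow for children on that side of the line.

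**4. How far from the spleen line?** With a proportional reduction r, volume falls below 5 MN if baseline is under 5/(1 - r).
- r = 0.10 (assumed): 5/0.90 = 5.56 MN.
- r = 0.253 (mean decrease in 5 adults over 26 weeks, Protocol 4.1): 5/0.747 = 6.69 MN.
- r = 0.40 (assumed): 5/0.60 = 8.33 MN.

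At r = 0.253, a baseline of 6.0 becomes 4.48 MN and fails; a baseline of 7.0 becomes 5.23 MN and does not. The unit of the adult figure is not stated, and it is applied to MN here only to show scale. SAP 2.8.1 divides volume by twice the body weight, so weight gain in a growing child also lowers MN.

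**5. How do other sections treat resumption?** Sections 8.3.3 (missed infusions) and 8.3.4.2 (potential dose-limiting toxicity) provide for re-dosing without mentioning the entry criteria. Section 10.5.3 does not list failure of the entry criteria as a reason to stop permanently. These are silences, and they sit in tension with 10.5.1 without contradicting it.

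**The case against.** The strongest reply is that nobody would apply 10.5.1 this way. Section 7.1 is framed as entry criteria, 10.5.1 concerns interruptions for suspected adverse events, the test is the investigator's best medical judgment, and Section 10.5 leans towards continuing. In context this reads as a safety recheck. Much of that stands, and it is why actual denial is unlikely. It does not remove the defect: 10.5.1 sends the reader to all of 7.1, and judgment about whether a criterion is met is not permission to ignore it. A height Z-score leaves little to judge.

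A second reply is that the sponsor must be consulted before restart, which would bring consistency across sites. This stands in part. The text limits the consultation to dose and escalation, and an investigator who has already concluded that the criteria are not met might not propose a restart.

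A reader might also count exposure to I 04 from the schedule. With the Week 26 infusion given and Weeks 28 and 30 missed, the earliest restart is Week 32, giving (64 - 32)/2 + 1 = 17 of the 33 infusion visits. The documents do not support that as a count of visits at which I 04 could be applied, because they do not show that the investigator holds an on-treatment MN value. The screening-only reporting in SAP 2.8.1 in fact favours an entry-only reading of I 04.

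**Conclusion.** The concern holds as a minor flaw in the wording of a rule, centred on I 05. Followed literally, 10.5.1 could withhold re-dosing from a child because of improvement, and nothing in either document exempts I 05 or I 04.

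The number affected cannot be estimated and is probably very small. It needs an investigator-decided gap of more than 1 infusion, a child who has crossed a threshold, and a literal reading. The spleen limits in the working rest on an adult mean or on assumed reductions; they show arithmetic and not risk.

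A reader might infer that failing the recheck ends participation, or that the protocol contradicts itself. Neither is supported. Under 10.5.2, permanent discontinuation needs a definitive decision by the investigator or patient, and Sections 8.3.3, 8.3.4.2 and 10.5.3 are merely silent. If a child were withheld drug, some data might still be recovered through the withdrawal visit (10.5.4) or the SAP 2.11.4 window of Days 275 to 456 for a missing Week 52 value. No effect on the primary safety conclusion is claimed.

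**What to change.** Add one sentence to Protocol 10.5.1: inclusion criteria I 04 (spleen volume) and I 05 (height Z-score) apply at study entry only and need not be met when treatment is re-initiated. Leave the rest of the recheck as it is. Rewriting it around an unnamed set of relevant safety criteria would create new room for interpretation and could drop I 01 (consent and assent) or I 03 (enzyme deficiency) without reason.

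The cost is a short amendment, with IRB/IEC approval before implementation under Section 15. It can be bundled with the next amendment. It needs no new data, patients or analyses.

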### **10.5.2 Permanent treatment discontinuation with investigational medicinal product(s)**

Permanent treatment discontinuation is any treatment discontinuation associated with the definitive decision from the investigator or the patient not to re-expose the patient to the IMP at any time.

#### **10.5.3 List of criteria for permanent treatment discontinuation**

The patient may withdraw from treatment with the IMP if he/she decides to do so, at any time and irrespective of the reason, or this may be the investigator's or sponsor's decision. All efforts should be made to document the reasons for treatment discontinuation and this should be documented in the e-CRF.

Patients should discontinue the IMP for the following reasons:

- Unacceptable toxicity (see [Section 8.3.4.2](#)).
- The need for intervention or therapy precluded by protocol, and determination by the investigator that it is medically necessary to do so.
- Patient noncompliance with treatment or if the patient wishes to be withdrawn from treatment.
- The patient is no longer deriving clinical benefit, in the opinion of the investigator.
- Pregnancy

In addition, the sponsor may decide to discontinue the trial prematurely for any other reason.

Any abnormal laboratory value or ECG parameter relevant to the situation will be immediately rechecked for confirmation before making a decision of permanent discontinuation of the IMP for the concerned patient.

#### **10.5.4 Handling of patients after permanent treatment discontinuation**

If a patient or parent/legal guardian decides to discontinue participation in the study, he should be contacted by the study investigator in order to obtain information about the reason(s) for discontinuation and collection of any potential AEs.

When possible, all tests and evaluations listed in [Section 1.2](#) for the post treatment withdrawal visit should be carried out within 2 weeks of the last olipudase alfa infusion. If a patient fails to return for the necessary visits, every effort must be made to contact the patient and determine the reason(s) and recorded on the e-CRF.

In all cases, the sponsor must be notified of all study terminations as soon as possible and the reason for and date of withdrawal from the study must be recorded in the e-CRF and in the patient's medical record.

#### **10.5.5 Procedure and consequence for patient withdrawal from study**

If possible, the patients are assessed using the procedure indicated for study withdrawal in [Section 1.2](#).

For patients who fail to return to the site, the investigator should make the best effort to contact the patient (eg, contacting patient's family or private physician, reviewing available registries or health care databases), and to determine his/her health status, including at least his/her vital status. Attempts to contact such patients must be documented in the patient's records (eg, times and dates of attempted telephone contact, receipt for sending a registered letter).

The statistical analysis plan (SAP) will specify how these patients lost to follow-up for their primary endpoints will be considered.

#### **10.5.6 Replacement of patients**

The minimum number of patients to be evaluated by age cohort is specified in [Section 6.1](#). Once these are met, if a patient prematurely discontinues the study after tolerating 2 consecutive doses of olipudase alfa at 0.3 mg/kg, an additional patient may be enrolled.

